6.1.2.1.4 Stable Disease (SD)

Neither sufficient shrinkage to qualify for PR nor sufficient increase to qualify for PD.

6.1.2.2 Non-target Lesions

All other lesions or sites of disease. Measurements of these lesions are not required, but the presence or absence of each should be noted throughout follow-up.

6.1.2.2.1 Complete Response (CR)

The disappearance of all nontarget lesions and normalization of tumor marker levels, if applicable.

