6.1.1.1.2 Neck lymph nodes

- Neck lymph nodes are considered pathologic and measurable if short axis ≥ 15 mm.
- Neck lymph nodes are considered pathologic but non-measurable if short axis ≥ 10 mm but < 15 mm.
- Neck lymph nodes are considered non-pathologic and non-measurable if short axis < 10 mm.

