6.1.2.1.1 Complete Response (CR)

The disappearance of the primary tumor and the resolution of pathologic neck adenopathy. For the definition of

radiographic complete response in the neck, the resolution of neck lymph nodes to < 10 mm in short axis diameter with non-pathologic appearance is sufficient.

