6.1.2.2.2 Partial Response (PR)/Stable Disease (SD)

The persistence of one or more nontarget lesion(s).

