6.2.2 Clinical Examination

Evaluation of measurable disease in the primary site as well as nodal sites by ENT examination should be recorded at baseline. Determination of complete response will occur through radiologic imaging as well as the post-protocol endoscopic examination.

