6.2.4 FDG-PET Scan

The ideal post-chemoradiotherapy response assessment method would accomplish two goals: 1) accurately detect viable residual disease amenable to surgical consolidation and 2) be prognostic for longer term clinical outcomes including PFS. Head and neck clinical examination alone has an accuracy of less than 50% for residual neck nodal disease,²⁷ while post-radiation diagnostic CT has higher sensitivity than clinical exam but unsatisfactory specificity.^{28,29} An increasing body of literature suggests that post-chemoradiotherapy positron emission tomography (PET), performed 8-12 weeks following completion of radiotherapy has improved accuracy relative to CT for classification of complete response in PULA HNSCC. The negative predictive value (NPV) for determination of residual neck disease, in particular, ranges from 92-100%.³⁰⁻³³ The University of Pittsburgh institutional experience indicates that serial PET/CT scans permit safe deferral of planned neck dissection following chemoradiotherapy.

Moreover, a PET scan added to a diagnostic contrasted CT is superior to clinical examination or diagnostic CT alone (utilizing RECIST criteria 1.0) with regard to correlation with PFS.³⁴ However, RECIST 1.0 criteria were developed primarily for response assessment in the metastatic solid tumor setting, where patients are treated with palliative systemic therapy. RECIST 1.0 criteria inadequately address the post-chemoradiotherapy setting. Specifically, a CR in accordance with RECIST 1.0 requires disappearance of all target lesions, including pathologic lymph nodes. However, non-pathologic, subcentimeter lymphadenopathy can persist after chemoradiotherapy. RECIST 1.1 now incorporates new guidelines for the measurement of nodal disease, and for determination of CR, a short axis of < 1 cm is no longer considered residual disease. The accuracy of the RECIST 1.1 criteria for assessment of residual disease or as a predictor of PFS following chemoradiotherapy for PULA HNSCC is not reported.

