6.3 Complete Response: Modified RECIST 1.1 (see section 6.1)

- Disappearance of primary tumor. Irregular contour of the tumor bed is consistent with radiation change
- Decrease in measurable pathologic neck lymph nodes to short axis measurement < 10 mm and non-necrotic appearance with normalization of nodal configuration. Increased enhancement may be attributable to radiation change.
- No new pathologic lesions

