8.3.1.2 Evaluation by an Otolaryngologist using Endoscopy as Indicated

The patient will be evaluated by the otolaryngologist 12-14 weeks following completion of cisplatin-IMRT (during weeks 20-22). Endoscopy for oropharyngeal or unknown primary carcinoma will be performed for response assessment as clinically indicated and is at the discretion of the surgeon. The surgeon will evaluate the need for primary site biopsy and/or neck dissection.

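### Non-target neck nodes must disappear for complete response, while the protocol elsewhere accepts nodes under 10 mm; the two rules need to be aligned

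*Combined protocol and SAP*

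**What the plan says.** **Which nodes are non-target.** Section 6.1.1.1.2 sorts neck nodes by short axis: 15 mm or more is pathologic and measurable, and under 10 mm is neither. In between, "Neck lymph nodes are considered pathologic but non-measurable if short axis" is at least 10 mm but under 15 mm. Section 6.1.2.1 limits target nodes to five. Section 6.1.2.2 makes all remaining disease non-target, does not require it to be measured, and asks only that its presence or absence be noted.

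**CR for non-target disease.** Section 6.1.2.2.1 requires "The disappearance of all nontarget lesions and normalization of tumor marker levels, if applicable". Section 6.1.2.2.2 assigns PR/stable disease for "The persistence of one or more nontarget lesion(s". Neither names lymph nodes or gives a size limit. In Table 9 (section 6.1.3), target CR with an incomplete non-target response and no new lesion is an overall PR.

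**CR for nodes elsewhere.** Under the Target Lesions heading, section 6.1.2.1.1 accepts, for radiographic CR in the neck, "the resolution of neck lymph nodes to < 10 mm in short axis diameter" if the appearance is non-pathologic. Section 6.3 repeats this for measurable nodes: "Decrease in measurable pathologic neck lymph nodes to short axis measurement < 10 mm". Section 6.2.4 gives the reason: "However, non-pathologic, subcentimeter lymphadenopathy can persist after chemoradiotherapy".

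**Endoscopy.** Section 6.2.2 states: "Determination of complete response will occur through radiologic imaging as well as the post-protocol endoscopic examination". Section 8.3.1.2 requires an otolaryngologist's evaluation, but endoscopy "will be performed for response assessment as clinically indicated and is at the discretion of the surgeon".

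**The concern.** The protocol applies two standards to nodes in the same neck. A node large enough at baseline to be a target counts as resolved below 10 mm. A smaller pathologic node, or one beyond the cap of five, must disappear on the literal rule. A patient's CR status can then turn on whether a node was classed as target or non-target at baseline, when its residual size is the same.

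The rule also invites inconsistent coding. Because non-target lesions need not be measured, one reader may record a visible 6 mm node as present and another may treat it as resolved, and both can cite the protocol.

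At stake are the recorded best overall response, the duration of CR (section 6.1.3.4), and those exploratory analyses that use clinical response (sections 9.4.1, 9.4.5, 9.4.8 and 10.4).

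A smaller, separate point is that section 6.2.2 makes endoscopy part of determining CR, section 8.3.1.2 leaves endoscopy to the surgeon, and nothing says how CR is assigned when it is not done.

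**Working it through.** The plan gives no figure on this point, so the check is to apply its own rules to example patients.

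**Step 1: two patients with the same residual node.** In both, all other target disease is in CR and there are no new lesions. The node sizes are illustrative.

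- Patient A has a 12 mm node at baseline. It is pathologic but non-measurable (6.1.1.1.2), hence non-target (6.1.2.2). It shrinks to 6 mm. It has not disappeared, so 6.1.2.2.1 is not met and 6.1.2.2.2 applies. Table 9 gives **PR**.
- Patient B has a 16 mm node at baseline. It is measurable and is selected as a target. It shrinks to 6 mm with non-pathologic appearance, which satisfies 6.1.2.1.1. With no non-target disease outstanding, the overall response is **CR**.

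**Step 2: vary the residual size of a non-target node**, with target CR and no new lesion. The last column assumes non-pathologic appearance.

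| Residual short axis | Literal 6.1.2.2.1 | Under-10 mm criterion applied to all nodes |
|---|---|---|
| 0 mm | CR | CR |
| 6 mm | PR | CR |
| 9 mm | PR | CR |
| 11 mm | PR | PR |

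The two readings differ only for a node that is still visible but below 10 mm.

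**Step 3: who can be affected.** In Table 9, a target PR with any non-progressing non-target disease is PR in any case, and target stable disease stays stable disease. The conflict therefore matters only when target disease is in CR and at least one non-target node remains visible below 10 mm. A patient whose pathologic nodes are all targets is scored CR under 6.1.2.1.1. The documents give neither the share of patients with non-target nodes nor the share of such nodes that remain visible, so no frequency can be calculated.

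**Step 4: what depends on it.** PFS is counted to progression or death (6.1.3.7), and the progression rules (6.1.2.1.3 and 6.1.2.2.3) do not use the CR/PR boundary. The sample size in section 10.2 (45 evaluable patients, 65% against 81% two-year PFS) uses PFS alone. Response is not a listed primary or secondary objective (2.1, 2.2, 10.1).

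**The case against.** The strongest case is that the intended rule is clear from context. Section 6.1.1.1.2 calls any node under 10 mm non-pathologic, so a 6 mm residual could fairly be recorded as absent. The sentence in 6.1.2.1.1 speaks of the neck as a region, and the note to Table 9 has the primary and the neck reported separately. The criticism in 6.2.4 is aimed at RECIST 1.0; the same section adds that RECIST 1.1 no longer counts a short axis below 1 cm as residual disease, and 8.3.1.1 requires RECIST 1.1. This is good evidence of intent. It does not remove the conflict: the non-target rule as written has no nodal exception, 6.3 confines the allowance to measurable nodes, and 6.1.2.2 does not require the measurement on which the lenient reading depends.

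The objection does rule out several stronger readings:

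- A reader might infer that patients with fully normalised necks are scored PR. No section says so. It follows only from the literal non-target rule, and only for patients with non-target nodes.
- A reader might infer a large loss in the CR rate. Any percentage would need the two shares missing in Step 3 and a true CR rate, none of which the documents supply.
- A reader might infer a bias tied to N stage. The documents do not link nodes of 10 to under 15 mm to N stage.
- A reader might infer that the correlative results are distorted. Those sections refer to clinical response without defining the groups. If CR and PR are pooled as responders, a shift between them changes nothing.

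On endoscopy, the CR definition in 6.3 does not list it and no text denies CR without it. The natural reading is that it contributes when performed. That leaves a wording mismatch with no demonstrated effect.

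**Conclusion.** The inconsistency is real and limited. A stated rule for non-target disease contradicts the nodal standard the protocol uses elsewhere, so this is more than a missing detail. On the literal rule, some patients with non-target nodes would be recorded as PR where the protocol's own nodal criterion gives CR. That conclusion assumes readers apply the requirement for disappearance as written; readers who follow the other nodal sections would record CR.

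The effect is confined to recorded best response, CR duration and, if the groups separate CR from PR, the exploratory analyses by clinical response. PFS, sample size and power are unaffected. The number of patients concerned cannot be derived from the documents. The endoscopy mismatch is a minor reconciliation.

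**What to change.** - **6.1.2.2.1:** state that non-target neck nodes are in CR when all are under 10 mm in short axis with non-pathologic appearance, and keep disappearance for all other non-target lesions.
- **6.1.2.2.2:** define persistence for neck nodes as failure to meet that same criterion.
- **6.3:** extend the nodal criterion from measurable nodes to all pathologic neck nodes.
- **6.1.2.2:** record the short axis of non-target neck nodes at baseline and on the response scans already scheduled.
- **6.2.2 and 8.3.1.2:** reconcile the two by stating how CR is assigned when endoscopy has not been performed. This need not change when endoscopy is done.

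The cost is an amendment to wording and slightly more reading work, with no added scan or procedure. Some responses that the literal rule would record as PR become CR, so the change is best made before responses are coded; recoding afterwards in an open-label trial would be harder to defend.

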6.1.2.2.2 Partial Response (PR)/Stable Disease (SD)

The persistence of one or more nontarget lesion(s).

6.1.2.2.3 Progressive Disease (PD)

The appearance of one or more new lesion(s) and / or unequivocal progression of existing non target lesions.

6.1.2.3 Symptomatic Deterioration

Patients with a global deterioration of health status requiring discontinuation of treatment without objective evidence of disease progression at that time should be classified as having *symptomatic deterioration*.

6.1.3 Evaluation of Patient's Best Overall Response

The best overall response is the best response recorded from registration until disease progression/recurrence, taking as reference for progressive disease the smallest measurements recorded since registration. Table 9 below provides overall responses for all possible combinations of tumor responses in target and nontarget lesions, with or without new lesions.

To be assigned a status of stable disease, measurements must have met the stable disease criteria at least once after study entry at a minimum interval of eight weeks.

Table 9. Overall Response for all Possible Combinations of Tumor Response

Target Lesions	Nontarget Lesions	New Lesions	Overall Response
CR	CR	No	CR
CR	Incomplete response/SD	No	PR
PR	Non-PD	No	PR
SD	Non-PD	No	SD
PD	Any	Yes or No	PD
Any	PD	Yes or No	PD
Any	Any	Yes	PD

CR = complete response; PR = partial response; SD = stable disease; PD = progressive disease

NOTE: BOTH CLINICAL (by ENT examination) AND RADIOGRAPHIC RESPONSE (by CT or MRI scan) will be recorded. Response in the primary and the neck will be reported separately.

6.1.3.1 First Documentation of Response

The time between initiation of therapy and first documentation of PR or CR.

6.1.3.2 Confirmation of Response

To be assigned a status of complete or partial response, changes in tumor measurements must be confirmed by repeat assessments performed no less than four weeks after the criteria for response are first met.

6.1.3.3 Duration of Response

Duration of overall response - the period measured from the time that measurement criteria are met for complete or partial response (whichever status is recorded first) until the first date that recurrent or progressive disease is objectively documented, taking as reference the smallest measurements recorded since treatment started.

6.1.3.4 Duration of Overall Complete Response

The period measured from the time measurement criteria are met for complete response until the first date that recurrent disease is objectively documented.

6.1.3.5 Duration of Stable Disease

A measurement from registration until the criteria for disease progression is met, taking as reference the smallest measurements recorded since registration. To be assigned a status of stable disease, measurements must have met the stable disease criteria at least once after study entry at a minimum interval of six weeks.

6.1.3.6 Survival

Survival will be measured from the date of entry on study.

6.1.3.7 Time to Progression and Progression-free survival

This interval will be measured from the date of entry on the study to the appearance of new metastatic lesions or objective tumor progression.

Progression-free survival (PFS) will be calculated from treatment initiation to disease progression or death from any cause or last follow up.

6.2 Methods of Measurement

Imaging based evaluation is preferred to evaluation by clinical examination. The same imaging modality must be used throughout the study to measure disease.

6.2.1 CT and MRI

CT and magnetic resonance imaging (MRI) are the best currently available and most reproducible methods for measuring target lesions. Conventional CT and MRI should be performed with contiguous cuts of 10 mm or less in slice thickness. Spiral CT should be performed by use of a 5 mm contiguous reconstruction algorithm. This specification applies to tumors of the chest, abdomen, and pelvis, while head and neck tumors, and those of the extremities require specific procedures.

6.2.2 Clinical Examination

Evaluation of measurable disease in the primary site as well as nodal sites by ENT examination should be recorded at baseline. Determination of complete response will occur through radiologic imaging as well as the post-protocol endoscopic examination.

6.2.3 Cytology and Histology

Cytologic and histologic techniques can be used to differentiate between complete and partial response in rare cases (e.g., after treatment to differentiate residual benign lesions and residual malignant lesions in germ cell tumors).

Cytologic confirmation of the neoplastic nature of any effusion that appears or worsens during treatment is required

when the measurable tumor has met response or stable disease criteria.

Should primary site biopsy, primary site salvage, and/or neck dissection be conducted, the pathologic response will be recorded.

6.2.4 FDG-PET Scan

The ideal post-chemoradiotherapy response assessment method would accomplish two goals: 1) accurately detect viable residual disease amenable to surgical consolidation and 2) be prognostic for longer term clinical outcomes including PFS. Head and neck clinical examination alone has an accuracy of less than 50% for residual neck nodal disease,²⁷ while post-radiation diagnostic CT has higher sensitivity than clinical exam but unsatisfactory specificity.^{28,29} An increasing body of literature suggests that post-chemoradiotherapy positron emission tomography (PET), performed 8-12 weeks following completion of radiotherapy has improved accuracy relative to CT for classification of complete response in PULA HNSCC. The negative predictive value (NPV) for determination of residual neck disease, in particular, ranges from 92-100%.³⁰⁻³³ The University of Pittsburgh institutional experience indicates that serial PET/CT scans permit safe deferral of planned neck dissection following chemoradiotherapy.

Moreover, a PET scan added to a diagnostic contrasted CT is superior to clinical examination or diagnostic CT alone (utilizing RECIST criteria 1.0) with regard to correlation with PFS.³⁴ However, RECIST 1.0 criteria were developed primarily for response assessment in the metastatic solid tumor setting, where patients are treated with palliative systemic therapy. RECIST 1.0 criteria inadequately address the post-chemoradiotherapy setting. Specifically, a CR in accordance with RECIST 1.0 requires disappearance of all target lesions, including pathologic lymph nodes. However, non-pathologic, subcentimeter lymphadenopathy can persist after chemoradiotherapy. RECIST 1.1 now incorporates new guidelines for the measurement of nodal disease, and for determination of CR, a short axis of < 1 cm is no longer considered residual disease. The accuracy of the RECIST 1.1 criteria for assessment of residual disease or as a predictor of PFS following chemoradiotherapy for PULA HNSCC is not reported.

To date, the majority of PET/CT literature conducted has been retrospective. The sole prospective study of PET/CT versus CT for first response assessment following chemoradiotherapy was performed at MDACC.³⁰ This study found that PET/CT was not superior to diagnostic CT alone for the accuracy of response assessment in unselected PULA HNSCC patients. However, in high risk patients defined as HPV-negative, non-opharynx, and/or tobacco-exposed, PET/CT outperformed CT. The study has been criticized for lack of integration of a diagnostic contrasted CT into the PET/CT acquisition algorithm, although PET/CT results were interpreted with knowledge of a separate contrasted diagnostic CT; such integration enhances per-lesion sensitivity and specificity in head and neck cancer staging³⁵ and is of theoretical utility in the post-treatment patient. The CT criteria used in the MDACC study to classify nodal disease were clinical and related to RECIST. However, long axis nodal measurements were utilized with the following categorization:

- Pathologic (residual disease) nodes: > 15 mm in longest diameter and/or necrotic appearance
- Indeterminate nodes: 10-15 mm in longest diameter and non-specific CT findings
- Non-pathologic nodes: < 10 mm in longest diameter and non-necrotic (CR)

At the University of Pittsburgh, the standard of care following definitive chemoradiotherapy for PULA HNSCC has been integrated PET/CT. Following PET/CT patients are placed into four clinical categories: Negative PET/CT (Complete Response); Probably Negative PET/CT (Low clinical concern; follow up indicated); Probably Positive PET/CT (Clinical concern; tissue sampling indicated); Positive PET/CT (Definite residual disease). This categorization has been found to correlate with clinical outcomes, specifically PFS.³⁶

Definition of CR following chemoradiotherapy therefore has two relevant, literature-based definitions which may be of clinical utility: 1) Quantitative anatomic criteria (RECIST 1.1); 2) Integrated PET/CT criteria.

6.3 Complete Response: Modified RECIST 1.1 (see section 6.1)

- Disappearance of primary tumor. Irregular contour of the tumor bed is consistent with radiation change
- Decrease in measurable pathologic neck lymph nodes to short axis measurement < 10 mm and non-necrotic appearance with normalization of nodal configuration. Increased enhancement may be attributable to radiation change.
- No new pathologic lesions

7. DRUG INFORMATION

7.1 Pembrolizumab

7.1.1 Study Drug Materials

Pembrolizumab drug substance is produced at two locations to yield: 1) a partially formulated aqueous solution stored under refrigerated conditions (2-8°C) at a concentration of 40-50 mg/mL in 10 mM histidine buffer, pH 5.2-6.8, and 2) a fully formulated aqueous solution stored frozen (-40°C) at a concentration of 22.5-27.5 mg/mL in 10 mM histidine buffer, pH 5.2-5.8 containing 7% sucrose and 0.02% polysorbate 80. The drug products are sterile filtered into Type I glass vials intended for single use.

Two drug product dosage forms are available for pembrolizumab: 1) a white to off-white lyophilized powder, 50 mg/vial, and 2) a liquid, 100 mg/vial.

- Pembrolizumab Powder for Solution for Infusion, 50 mg/vial (manufactured using the partially formulated drug substance), is reconstituted with sterile water for injection prior to use. It is formulated with L-histidine as buffering agent, polysorbate 80 (surfactant), sucrose as stabilizer/tonicity modifier, and hydrochloric acid (HCl) and/or sodium hydroxide (NaOH) for pH adjustment (if necessary).
- Pembrolizumab Solution for Infusion, 100 mg/vial is a liquid drug product (manufactured using the fully formulated drug substance), and has the identical formulation as that of the reconstituted lyophilized vial.

The product after reconstitution with sterile water and the liquid drug product are a clear to opalescent solution which may contain proteinaceous and extraneous particulates.

Both the pembrolizumab reconstituted product and the liquid product are intended for IV administration and both can be further diluted with normal saline in IV containers made of polyvinyl chloride (PVC) or non-PVC material.

